After enrollment, the participants will be randomized in a 1:1 ratio having either oropharyngeal swab performed including the posterior oropharyngeal wall and both palatine tonsils (intervention group) or only including the posterior oropharyngeal wall and avoiding the palatine tonsils (control group), see Figure B.

A block randomization list was generated by [name] using an online randomization software⁽⁷⁾ afterward uploaded to REDCap. The randomization group will be disclosed in connection with trial registration in REDCap using the REDCap “randomize” function. The oropharyngeal sample will afterward be performed by the trained healthcare workers with or without the palatine tonsils depending on the randomization to either the intervention or control group.

Figure B. Study flowchart.

The swabs will be placed in separate tubes dry and sent to the clinical microbiology laboratory for detection of SARS-CoV-2 by single-target RT-PCR at Statens Serum Institute. Samples with viral cycle threshold (Ct) values below 38 are considered positive, 38-40 inconclusive and above 40 negative⁽⁸⁾.

All participants are required to fill out a survey on-site about their reason for being tested, prior Covid-19 infection(s), vaccinations status, symptoms, and if any prior tonsillectomy has been performed (appendix 2).

All healthcare workers participating in the data collection have been given a unique ID which will be registered for each OPS performed in the study. Further, the healthcare worker will also be asked to rate the Mallampati score of the participants including in the study (appendix 5).

All data will be documented on-site in a secure web database (REDCap, appendix 3).

Outcomes

The primary outcome will be reported as:

- SARS-CoV-2 RNA by RT-PCR test result (positive, negative, inconclusive)

The secondary outcome will be reported as:

- SARS-CoV-2 RT-PCR cycle threshold (Ct) value
- Test discomfort on a 11-point NRS-scale
- Development of COVID-19 disease after testing
- SARS-CoV-2 detection rate for each healthcare worker
- Mallampati Score of participants being tested

Sample size

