Based on a SARS-CoV-2 test positive proportion on 13% in the Danish capital region the last week of October 2022, we expected proportion of positive to increase to about 20% during the following study period⁽⁹⁾. The power calculation was based on an expected improvement in diagnostic accuracy of 25% by including the palatine tonsils in the oropharyngeal specimen collection compared to a sample without the tonsils. We therefore estimated that a sample of 2,188 participants (with about 438 with SARS-CoV-2 infection) would provide the trial with 80% power at a 5% significance level with an expected test positive proportion of 20% for SARS-CoV-2

among the participants tested ⁽¹⁰⁾. As we expect about 10% missing due to dropout and missing data, we aim to include 2,407 participants in the study. All individuals entering the testing facility who meet the eligibility criteria are offered to participate in the study. We expect about 300-700 tests performed at both COVID-19 test centers each day and an assumed participation at 10-30%. We therefore expect to complete the study within two-three months.

Statistical analysis

A study participant is considered to have a SARS-CoV-2 infection if the oropharyngeal sample is RT-PCR positive (reference standard). Participants with an inconclusive RT-PCR test result will be included in the analyses as a negative test result following an intention-to-diagnose approach⁽¹¹⁾. Differences in the proportion of SARS-CoV-2 positive tests between the intervention and the control group will be compared using binary logistic regression using test center as fixed effect and a generalized estimating equation to adjust for clustering of data within the healthcare workers performing the sample. The difference in SARS-CoV-2 detection rate between healthcare workers will also be reported separately to estimate the inter-person variance. The Ct values from positive RT-PCR samples and the NRS discomfort scores will be compared using a general linear model with mixed effects (Ct) and GEE models (NRS discomfort). The 95% confidence intervals (CI) will be presented. Categorical data will be summarized with number and percentage while continuous data will be summarized by mean and standard deviation. We will not perform tests of statistical significance for baseline characteristics. 5% significance level was applied. Statistical Analysis Software ver. 9.4 (SAS Institute, North Carolina, U.S.) was used for the statistical analyses.

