Planned subgroup analyses

We planned to do a sensitivity analysis using a lower cycle threshold (Ct) < 25 for positive SARS-CoV-2 definition to explore the consequences of a higher test specificity for the SARS-CoV-2 detection rate between specimen types. We also plan to estimate the sensitivity and specificity using Bayesian latent class analysis for accounting for an imperfect reference standard. Further, we planned to do subgroup analyses exploring the distribution of positive test results for participants stratified by symptoms, previous COVID-19 infection, vaccinations status, prior

tonsillectomy and Mallampati score. To explore a potential bias from the distribution of the inconclusive test results, we excluded the inconclusive results in a subgroup analyses.

Quality assurance

All the healthcare workers who will be including participants for this study will be trained and have at least three months prior experience in oropharyngeal swabs. Further, they will complete a special standardized training- and certification program taught by a board-certified otorhinolaryngologist to ensure all healthcare workers perform the same technique on the participants in the intervention and control group. A two-hour long training session will cover the theoretical and practical part of oropharyngeal sample techniques and the study design with following elements:

- A walk-through of the practical study setup and how participants are enrolled, and diagnostic interventions are performed
- Theory on oropharyngeal swabbing including upper airway anatomy and anatomical variations/Mallampati Score.
- Practical exercises in oropharyngeal swab technique.

Checklists outlining the two different sampling techniques for oropharyngeal swabs with and without palatine tonsils, respectively, will be used to assess the swab performance of all the healthcare workers by a board-certified otolaryngologist or special trained nurse before study enrollment (see appendix 1).

An on-site healthcare professional is in charge of internal daily quality assurance ([name]).

Follow-up

The participants enrolled in the study will be asked to agree to be contacted in case of a positive test result. About one month after a positive test results the participants will receive an online questionnaire or phone call to follow up. The follow-up questions can be found in appendix 3.

Ethics and safety considerations

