Appendix 2: Survey for participants

Survey to be filled out by participant

1. Are you vaccinated against COVID-19?

YES

NO

2. Have you previously been infected with COVID-19?

YES

NO

3. Please indicate your reason for getting tested today:

Symptoms

Close contact

Positive quick test

Screening

Test ahead of social gathering or nursing home visit

Other

If 'yes' to symptoms, which symptoms do you have?

Sore throat

Headache

Cough

Muscle and joint pain

Fever

Fatigue

Reduced sense of smell or taste

If "yes" to symptoms, for how many days have you had symptoms?

Indicate number of days: _____ day(s)

4. Have you had your tonsils removed??

YES

NO

5. On a scale from 0-10, how uncomfortable was today's test for COVID-19?

No discomfort

Worst possible discomfort

To be filled out by personnel:

REDCap ID: _____

Personnel ID: _____

Participant's Mallampati score:

1

2

3

4

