Appendix 3: REDCap database

REDCap-ID	
Date	DD-MM-YYYY
Randomization	Oropharyngeal swab including palatine tonsils Oropharyngeal swab excluding palatine tonsils
CPR-number	
Sample ID	
Are you vaccinated against COVID-19?	YES NO
Have you previously been infected with COVID-19?	YES NO
Please indicate your reason your reason for getting tested today	Symptoms Close contact Positive quick test Screening Test ahead of social gathering / visit to a nursing home Other
If "YES" to symptoms, what symptoms do you have?	Sore throat Headache Cough Muscle and joint pain Fever Fatigue Reduced sense of smell or taste
If "YES" to symptoms, for how many days have you had symptoms?	
Have you had your tonsils removed?	YES NO
On a scale from 0-10, how uncomfortable was today's test for COVID-19?	0 1

	2 3 4 5 6 7 8 9 10
Personnel ID	
Participant's Mallampati score	1 2 3 4
FOLLOW UP	
Have you since the test and until four weeks later had symptoms of COVID-19?	YES NO
If 'yes' to symptoms, when did you develop symptoms?	I had symptoms when I got tested I developed symptoms 1-3 days after the test I developed symptoms 3-5 days after the test I developed symptoms 5-7 days after the test I developed symptoms 1-2 weeks after the test I developed symptoms 2-3 weeks after the test I developed symptoms 3-4 weeks after the test I do not know / I do not wish to disclose
If 'yes' to symptoms, which symptoms did you develop?	Sore throat Headache Cough Muscle- / joint pain Fever Fatigue Reduced sense of smell / taste Other
If 'yes' to fever, what was your highest temperature?	

If 'yes' to fever, how many days did you have a fever for?	
If 'yes' to symptoms, how many days did you have symptoms in total?	
Think about period from one week before your test until four weeks after. Which of the following statements describes best how you felt at your worst?	
I had no symptoms
 
I was sick and stayed home
 
I was admitted to the hospital due to COVID-19

Have you taken days off work / from school during your infection with COVID-19?	
No, I have not taken any days off
 
Yes, I have taken days off between one week before the test until four weeks after
 
Yes, I have taken days off later than four weeks after
 
Not relevant

If 'yes' to having taken days off, how many days have you taken off in total?	
Do you smoke?	
Yes
 
No
 
I used to smoke, but I do not smoke anymore
 
Not relevant / I do not wish to disclose

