2.4 Withdrawal/Follow-up

The level of withdrawal and the missing final RT-PCR test results during the study will be tabulated. As they only had a single OPS performed, no dropouts will be expected after the intervention – beside missing data.

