3.1 Analysis methods

Analysis method and treatment effects

Differences in the proportion of SARS-CoV-2 positive tests between the intervention and the control group will be compared using binary logistic regression using test center as fixed effect and a generalized estimating equation to adjust for clustering of data within the healthcare workers performing the sample. The difference in SARS-CoV-2 detection rate between healthcare workers will also be reported separately to estimate the inter-person variance. The Ct values from positive RT-PCR samples and the NRS discomfort scores will be compared using a general linear model with mixed effects (Ct) and GEE models (NRS discomfort).

The 95% confidence intervals (CI) will be presented. The level of statistical significance will be defined as $p < 0.05$.

Adjustment for covariates

The regression analyses will be adjusted for the effect of the test centers and the individual health-care worker performing the sample.

Methods used for assumptions to be checked for statistical methods

Assumptions for the logistic regression analysis included a binary outcome, independent observations and linearity in logit for continuous variables. To account for lack of independent observations, a generalized estimating equation approach will be applied. No continuous variables will be included.

Assumptions for the linear regression analysis included a normal distribution, independent observations, equal variation (homoscedasticity) and linearity in logit for continuous variables. Normally distributed outcomes and homoscedasticity will be evaluated visually by plots of the residuals. To account for lack of independent observations, a generalized estimating equation approach and mixed effect models will be applied. No continuous variables will be included.

Details of alternative methods to be used if distributional assumptions do not hold, e.g., normality, proportional hazards, etc.

If the assumption of a normal distribution of the outcome in the linear regression model is not fulfilled, a transformation of the outcome will be applied (e.g., logarithmic and rank transformations).

Planned subgroup analyses

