We planned to do a sensitivity analysis using a lower cycle threshold (Ct) < 25 for positive SARS-CoV-2 definition to explore the consequences of a higher test specificity for the SARS-CoV-2 detection rate between specimen types. We also plan to estimate the sensitivity and specificity using Bayesian latent class analysis for accounting for an imperfect reference standard. Further, we planned to do subgroup analyses exploring the distribution of positive test results for participants stratified by symptoms, previous COVID-19 infection, vaccinations status, prior tonsillectomy and Mallampati score. To explore a potential bias from the distribution of the inconclusive test results, we excluded the inconclusive results in a subgroup analyses.

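### The planned Bayesian latent class analysis cannot estimate absolute sensitivity from one swab per person; its level would come mainly from unstated priors

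*Combined protocol and SAP*

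**What the plan says.** The latent class analysis is a single sentence, given in the protocol and repeated in the SAP, both times under Planned subgroup analyses: "We also plan to estimate the sensitivity and specificity using Bayesian latent class analysis for accounting for an imperfect reference standard". Nothing is said about the model, the indicators, the strata, conditional independence or the priors.

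Other sections fix what data such a model would have:

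- Protocol, Randomization to intervention and control group: each person is allocated 1:1 to one of the two techniques, and the swab is sent "for detection of SARS-CoV-2 by single-target RT-PCR at Statens Serum Institute".
- SAP 2.4: "As they only had a single OPS performed, no dropouts will be expected after the intervention".
- Protocol, Statistical analysis: the same swab result defines infection and is labelled the reference standard.
- Protocol, Follow-up: "The participants enrolled in the study will be asked to agree to be contacted in case of a positive test result".
- Appendix 2: the survey item "Please indicate your reason for getting tested today" offers symptoms and a positive quick test among its answers, and Appendix 3 carries the same list ("Close contact Positive quick test Screening"). A negative quick test is not recorded.
- SAP, Planned subgroup analyses: symptoms, prior infection and vaccination are used to stratify positive results. They are not assigned to the latent class model.

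**The concern.** A latent class model recovers sensitivity and specificity from agreement and disagreement among several imperfect indicators in the same people. Here each person has one. The reference standard cannot serve as the second, because it is the same swab. Follow-up cannot either, because it reaches only people who tested positive and so says nothing about missed infections.

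The analysis would still run, since a proper prior always gives a posterior. The risk is that the trial reports an absolute sensitivity for each technique, with an interval, that readers take as a finding when its level mainly reflects a prior that nobody stated in advance. The research question is phrased in terms of sensitivity, which makes that reading more likely.

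**Working it through.** **Inputs.** From the protocol's Sample size section: expected positive proportion 20%, improvement 25%, 2,188 participants, 80% power, 5% level. From the design: 1:1 allocation, one swab and one RT-PCR result per person. The priors, and specificity values other than 100%, are assumptions made here to show the range.

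**The plan's own figure.** Two proportions, 20% versus 25%, two-sided 5%, 80% power, no continuity correction: 1,094 per arm, 2,188 in total. This reproduces the plan, so 25% versus 20% is used as the assumed result (274/1,094 versus 219/1,094).

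**Model.** For arm *a* and stratum *s*, with prevalence π, sensitivity Se and specificity Sp:

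p(a,s) = π(s)·Se(a) + [1 − π(s)]·[1 − Sp(a)]

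With Sp = 100% this is π(s)·Se(a). Multiplying every prevalence by a constant and dividing both sensitivities by it leaves every p unchanged.

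**Rank check.** Rank of the matrix of derivatives of the observable proportions, against the number of parameters. Local identification needs the two to be equal.

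| Data in the model | Separate Sp | Common Sp | Sp = 100% |
|---|---|---|---|
| One swab, 1 stratum | 2/5 | 2/4 | 2/3 |
| One swab, 2 strata | 4/6 | 4/5 | 3/4 |
| One swab, 4 strata | 6/8 | 6/7 | 5/6 |
| One swab, 8 strata | 10/12 | 10/11 | 9/10 |
| Plus one indicator, 1 stratum | 5/7 | 5/6 | 4/5 |
| Plus one indicator, 2 strata, differing prevalence | 8/8 | 7/7 | 6/6 |
| Plus one indicator, 2 strata, equal prevalence | 6/8 | 6/7 | 5/6 |
| Plus two indicators, 1 stratum | 9/9 | 8/8 | 7/7 |

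The added indicators are taken as conditionally independent of the swab, with accuracy constant across strata. With the swab alone, no number of strata is enough.

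**Range that fits without any prior.** Let f = (1 − Sp)(1 − π). Then Se(tonsils) = (0.25 − f)/π and Se(control) = (0.20 − f)/π.

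- Sp = 100%: π = 25% gives 1.00 and 0.80; π = 50% gives 0.50 and 0.40; π = 100% gives 0.25 and 0.20. All fit equally well.
- Sp = 98%: Se(tonsils) = 1 at π = 0.23/0.98 = 0.235, where Se(control) = 0.79. The ranges are 0.25–1.00 and 0.20–0.79.

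**Effect of the prior.** Flat prevalence, common specificity Beta(99,1), importance sampling:

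| Prior on each sensitivity | Tonsil-arm sensitivity, median (95% interval) |
|---|---|
| Beta(8,8) | 0.55 (0.36–0.74) |
| Flat | about 0.63 (0.27–0.98) |
| Beta(16,4) | 0.86 (0.72–0.95) |
| Beta(18,2) | 0.95 (0.84–0.99) |

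The flat case has a closed form. With Sp = 100%, flat priors and large n, the posterior density of π is proportional to 1/π², so Se(tonsils) = 0.25/π is uniform on 0.25–1.00. Its median is 0.625 and its 95% interval is 0.25 + 0.025 × 0.75 = 0.269 to 0.25 + 0.975 × 0.75 = 0.981. At 10,940 per arm the simulated interval is still 0.27–0.98.

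**The ratio.** Under the flat sensitivity prior the interval for the sensitivity ratio narrows from 1.07–1.48 to 1.19–1.33 at ten times the size. The direct ratio is 0.25/0.20 = 1.25. With counts, SE of the log ratio = √(1/274 − 1/1,094 + 1/219 − 1/1,094) = 0.080, so the 95% CI is 1.07–1.46, ignoring clustering.

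The ratio does need a specificity assumption. If the common specificity also gets a flat prior, the upper limit for the ratio rises to about 20.

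**The case against.** The sentence is underspecified rather than demonstrably wrong. Two centres and one conditionally independent indicator could identify the model. Symptoms and reason for testing are collected from everyone at the visit, and relying on informative priors is a normal reason to go Bayesian. The secondary outcome of disease developing after the test is not restricted to positives, and Ct values and inconclusive results carry more than a yes or no. The quoted range is also stretched: it includes 100% prevalence, while the protocol's introduction cites 52–100% for oropharyngeal accuracy. Finally, the analysis is exploratory.

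Part of this stands. The failure is of the model as written, not of every possible model, and the analysis is indeed exploratory. A flat sensitivity prior on 0.52–1.00 gives a narrower 0.83 (0.62–0.99). It also stands that at the planned size the prior moves the ratio: 1.20 (1.04–1.40) under Beta(16,4) and 1.16 (1.01–1.35) under Beta(18,2).

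The rest does not rescue the analysis.

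- No indicator or stratum is assigned to the model. The two centres help only if their prevalences differ, and the conditional independence of symptoms would have to be argued.
- The later-disease outcome is collected through follow-up, and the protocol makes that contact only after a positive result.
- Ct values and inconclusive results come from the same swab.
- The 0.52–1.00 prior still sets the level. The control sensitivity must be at least 0.52, so the tonsil-arm sensitivity must be at least 0.52 × 1.25 = 0.65, and at ten times the size its interval is still 0.66–0.99.
- That the prior also shifts the ratio is a reason to estimate the ratio directly.

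**Conclusion.** The concern holds. As written, the latent class analysis cannot identify absolute sensitivity, even with specificity fixed at 100%, and neither a larger sample nor more strata would change that. If specificity may differ between techniques, it is not identified either. On the assumed 25% versus 20% result, the reported tonsil-arm sensitivity could have a median anywhere from 0.55 to 0.95 across four illustrative priors.

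The algebra depends only on one swab result per person with no other indicator in the model. The sizes depend on the assumed result and priors. The primary comparison of positive proportions is not affected, and the randomised arms answer the comparative question through relative sensitivity, provided the specificity assumption is stated. The change should be made before analysis, but it concerns one exploratory result.

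**What to change.** In both Planned subgroup analyses sections, replace the latent class estimates with relative sensitivity: the ratio of positive proportions, intervention over control, with a 95% CI that allows for healthcare-worker clustering. A log-link GEE would do this, keeping the structure SAP 3.1 already has ("using test center as fixed effect and a generalized estimating equation to adjust for clustering of data within the healthcare workers").

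Report the ratio over a pre-stated grid of prevalence and specificity that also lets specificity differ between arms. At 25% versus 20% positive, the ratio is (0.25 − f_T)/(0.20 − f_C), where f_T and f_C are f for the tonsil and control arms:

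| Specificity, tonsil / control | π = 25% | π = 50% | π = 90% |
|---|---|---|---|
| 100% / 100% | 1.25 | 1.25 | 1.25 |
| 98% / 98% | 0.235/0.185 = 1.27 | 0.240/0.190 = 1.26 | 0.248/0.198 = 1.25 |
| 98% / 100% | 0.235/0.200 = 1.18 | 0.240/0.200 = 1.20 | 0.248/0.200 = 1.24 |
| 100% / 98% | 0.250/0.185 = 1.35 | 0.250/0.190 = 1.32 | 0.250/0.198 = 1.26 |

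Equal specificity is therefore the key assumption and should be stated. The 98–100% range is an assumption made here; the sponsor should justify its own.

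If the latent class analysis is kept, fix its model, priors, strata and any further indicator before analysis, with the conditional-independence argument for that indicator. Show prior against posterior, add a prior-sensitivity analysis, and do not present absolute sensitivity as estimated from the trial data.

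The cost is SAP wording and a simpler exploratory analysis, with no new data. The sponsor gives up absolute accuracy figures that the data cannot support, and must show openly that unequal specificity can move the ratio to about 1.18–1.35 at 25% prevalence.

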3.1 Outcome definitions

The primary outcome:

- The proportion of positive SARS-CoV-2 RNA samples by RT-PCR for intervention and control group

The secondary outcome:

- SARS-CoV-2 RT-PCR cycle threshold (Ct) value
- Test discomfort on a 11-point NRS-scale
- Development of COVID-19 disease after testing
- SARS-CoV-2 detection rate for each healthcare worker
- Mallampati Score of participants being tested

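### Excluding inconclusive PCR results is a weak sole check on coding them negative; an analysis counting them as positive should be added beside it

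*Combined protocol and SAP*

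**What the plan says.** The protocol, under Randomization to intervention and control group, sets three result categories: "Samples with viral cycle threshold (Ct) values below 38 are considered positive, 38-40 inconclusive and above 40 negative". Its Statistical analysis section then fixes the primary handling: "Participants with an inconclusive RT-PCR test result will be included in the analyses as a negative test result following an intention-to-diagnose approach".

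The check on that handling is under Planned subgroup analyses, in the protocol and again in SAP 3.1 Analysis methods: "To explore a potential bias from the distribution of the inconclusive test results, we excluded the inconclusive results in a subgroup analyses".

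Two other analyses in the same paragraph touch on the definition of a positive result. One tightens the cut-off: "We planned to do a sensitivity analysis using a lower cycle threshold (Ct) < 25 for positive SARS-CoV-2 definition". The other is a latent class model: "We also plan to estimate the sensitivity and specificity using Bayesian latent class analysis for accounting for an imperfect reference standard". Neither fills the gap. At Ct below 25 the 38-40 band stays negative, and the text does not say how inconclusive results enter the latent class model. No planned analysis counts the band as positive.

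The protocol's Outcomes section names inconclusive as a category of the primary outcome: "SARS-CoV-2 RNA by RT-PCR test result (positive, negative, inconclusive". The SAP outcome is narrower: "The proportion of positive SARS-CoV-2 RNA samples by RT-PCR for intervention and control group".

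**The concern.** An inconclusive sample carries a late signal, just beyond the cut-off for positive. The plan recognises that the way such samples fall between the arms could matter, and it sets out to explore this. The analysis chosen for the purpose responds only weakly to an imbalance: it leaves the count of positives in each arm untouched and trims the denominators by a few per cent.

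It also selects participants on a result that the swab technique can influence, so the two groups compared are no longer the groups as randomised.

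The exclusion analysis could therefore look like confirmation of the primary result in a trial whose conclusion does depend on where the 38-40 band is placed. A reader would have no analysis showing the other end of the range.

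**Working it through.** **Inputs from the documents.** Control positivity 20%, a 25% relative improvement (so 25% with tonsils), 80% power, 5% significance, 1:1 allocation and 2,188 participants before the allowance for missing data (protocol, Sample size and Randomization).

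**Assumed.** A two-sided test, and the inconclusive rates, for which the documents give no figure. Write i for the inconclusive proportion in an arm and p for the proportion with Ct below 38.

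**The plan's own figure.** Pooled-variance formula, with mean proportion 0.225:

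n per arm = [1.960·√(2·0.225·0.775) + 0.842·√(0.20·0.80 + 0.25·0.75)]² / 0.05² = 1,093.7, rounded up to 1,094. Twice that is 2,188, as stated.

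**The three codings.**
- Negative: p
- Excluded: p/(1−i), a shift of about p·i
- Positive: p+i, a shift of i

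Exclusion is equivalent to assuming that inconclusive samples are positive at their own arm's rate, here 20-25%.

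**Worked case, inconclusive 4% control v 2% intervention** (unclustered pooled z test, 1,094 per arm):
- Negative: 20.0% v 25.0%; difference 5.00 points, SE 1.79, z=2.80, p=0.005; ratio 1.25.
- Excluded: 0.20/0.96 = 20.83% v 0.25/0.98 = 25.51%; difference 4.68, SE 1.83, z=2.55, p=0.011; ratio 1.22.
- Positive: 24.0% v 27.0%; difference 3.00, SE 1.86, z=1.61, p=0.11; ratio 1.125.

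Exclusion moved the difference by 0.32 points and recoding by 2.00, so exclusion shows 0.32/2.00 = 0.16 of the movement.

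**Range of assumed rates** (coded negative, the ratio is always 1.25, p=0.005):

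| Inconclusive, control v intervention | Excluded: ratio (p) | As positive: ratio (p) | Shift excluded / shift as positive |
|---|---|---|---|
| 2% v 1% | 1.24 (0.007) | 1.18 (0.029) | 0.16 |
| 4% v 2% | 1.22 (0.011) | 1.125 (0.11) | 0.16 |
| 5% v 2% | 1.21 (0.015) | 1.08 (0.29) | 0.18 |
| 10% v 5% | 1.18 (0.032) | 1.00 (1.00) | 0.18 |
| 3% v 3% | 1.25 (0.005) | 1.22 (0.007) | not applicable |
| 2% v 5% | 1.29 (0.001) | 1.36 (<0.001) | 0.30 |

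**Excess of control inconclusives at which p<0.05 is lost**, with 20% v 25% positive and 0-5% inconclusive in the intervention arm: about 1.2-1.5 percentage points if counted as positive, about 6.3-6.5 if excluded.

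These calculations leave out the test-centre term and clustering by healthcare worker.

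**The case against.** The strongest reply is that Ct below 38 is the endpoint, fixed in advance. If swabbing the tonsils turns a sample that would have read Ct 39 into one that reads 37, that is a real gain in detection at the stated cut-off, which is what the trial sets out to measure. Counting Ct 38-40 as positive changes the question to detection at Ct 40 or below. This stands. A reader might infer that the primary coding is biased, or that the recoded analysis would measure the bias; the documents support neither.

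The direction is also open. A reader might assume that controls will have more inconclusives. Tonsil swabbing could equally bring samples from above 40 into the band, and then the primary coding is conservative, as in the 2% v 5% row.

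Nor is exclusion an empty check. When rates differ it moves the same way as recoding, and it can tip a borderline result: with 20% v 23.5% positive and 2% v 1% inconclusive, p goes from 0.047 to 0.063. It is a legitimate intermediate scenario. The departure from the randomised groups affects this supplementary analysis only; the primary analysis keeps inconclusive participants in.

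If the protocol's three-category outcome is reported by arm, a crude as-positive comparison can be read from it. That meets part of the need, but the SAP does not carry it over, and a crude count lacks the planned adjustment for centre and healthcare worker.

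Finally, requiring both codings to reach significance would be a poor rule. At 24% v 27% with 1,094 per arm, power is about 36%, so the recoded analysis would often miss even with a true difference. Even at 3% v 3% the ratio falls from 1.25 to 1.22, so attenuation alone is not evidence of bias.

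**Conclusion.** The point holds as a limit on what the planned check can show. For the purpose the plan gives it, exclusion alone is weak: across the unequal assumed rates it shows about 0.16-0.30 of the movement that recoding as positive shows, and it selects on a post-randomisation result. At the design effect it kept p<0.05 in every scenario tabulated, while recoding lost it at 4% v 2%.

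The size rests on the plan's 20% v 25% and on assumed inconclusive rates. If inconclusive results are rare or evenly spread, little changes under any coding. A reader should not conclude that the primary analysis is wrong or that it exaggerates the benefit of tonsil swabbing. What is missing is the analysis that shows how far the conclusion depends on coding. Adding it is a worthwhile, cheap improvement.

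**What to change.** In Planned subgroup analyses, in the protocol and in SAP 3.1 Analysis methods:

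1. Keep the exclusion analysis.
2. Add an analysis that counts Ct 38-40 as positive (detection at Ct 40 or below) in all randomised participants with a PCR result, using the same logistic GEE model with test centre as fixed effect and clustering by healthcare worker.
3. Report the number of inconclusive results by arm.
4. Present the estimates and 95% CIs under the as-negative and as-positive codings side by side, described as limits on the dependence on coding when both arms are coded alike. Do not present them as an estimate of bias, and do not make significance under both codings a condition for the primary claim.

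The cost is one more run of an existing model, a sentence or two in each document and one line in a table. The drawback for the sponsor is that the statement on robustness may turn out less favourable.
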